Parameter	Description/Definition
Sociodemographic characteristics	Age, sex, complimentary universal health care (CMU-c), aid for complementary health care (ACS) for elderly patients, department of patient's residence
Medical history and comorbidities	Identified algorithmically with hospital diagnoses, active long-term disease, drugs and medical procedures: Coronary arterial diseases (CAD), Dementia (Alzheimer dementia/vascular dementia/other dementia), Ischemic or hemorrhagic stroke (intracranial bleeding) Congestive Heart failure, Peripheral arterial disease, Other vascular diseases; Sleep disorders; Active cancer (within 6 months in the historical period) Age adjusted Charlson Cormordity Index (ACCI) adapted to the SNDS data (20) ; Frail patient identified by Claims-Based Fragility Index (CFI) adapted to the SNDS data (21) ; Malnutrition ; Morbid Obesity; Anemia; COPD Diabetes Patients at risk of falls identified by an algorithm adapted to SNDS data (22) ; Patients poly-medicated Patient with at least one nursing home entry available
Drug exposure	AF patients exposed to VKA, apixaban, rivaroxaban, dabigatran AF patients unexposed to OAC
Associated treatments	Beta-blockers, antihypertensives, antiplatelet drugs, other anticoagulants, Non-steroidal anti-inflammatory drugs (NSAIDs), oral corticoids, proton pump inhibitors, Selective serotonin reuptake inhibitor antidepressants (SSRIs), systemic azole antifungals, medical procedure of cardioversion, CYP P450 inhibitors, protease inhibitors
Left atrial appendage (LAA) occlusion	Medical procedure of treatment of thromboembolic risk in AF in alternative of OAC
Modified risk scores in AF	Thromboembolic risk: Modified CHA ₂ DS ₂ VASC identified by an algorithm adapted to SNDS data Hemorrhagic risk: Modified HAS-BLED identified by an algorithm adapted to SNDS data

Parameter	Description/Definition
Annual standardized incidence rate of AF	Ratio of number of newly diagnosed non valvular AF patients to the number of individuals in the French population per calendar year (N per 100,000 inhabitants) standardized on age using the 2019 French population structure and 2020 in sensitivity analyses.
Annual prevalence of AF	Ratio of number of diagnosed NVAF patients to the number of individuals in the French population (INSEE data) per calendar year (N per 100,000 inhabitants).

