9.7.4.3 Estimation of the annual standardized incidence rate and prevalence

The analysis of annual standardized incidence rate and prevalence of diagnosed AF patients in France in 2016, 2017, 2018 and 2019 will be descriptive in nature and will be performed for each calendar year, from 2016 to 2020.

Prevalent and incident patients with an AF diagnosis will be the patients with a diagnosed NVAF during the historical period and the patients newly diagnosed AF during the inclusion period. The estimations of the prevalence and incidence of AF will be based on the count of patients living in France as denominator (based on socio-demographic data published by the National Institute for Statistics and Economic Studies (INSEE) and will be expressed per 100,000 inhabitants.

The analysis will include the following measures for summarizing the information on the prevalence and incidence of diagnosed AF patients, for each calendar year between 2016 and 2019 in France:

- Overall count of prevalent and incident of diagnosed AF patients in year Y, separately
- Overall crude prevalence and cumulative incidence of diagnosed AF patients in year Y, separately; computed as:

$$CP_Y = \frac{\text{count of prevalent diagnosed NVAF patients in year Y}}{\text{count of French adult residents from census data in year Y}} \times 100,000$$

- CP_Y represents the crude prevalence of diagnosed AF patients in the year Y
- Y represents the year of interest

$$CI_Y = \frac{\text{count of incident diagnosed NVAF patients in year Y}}{\text{count of patients at risk in year Y}} \times 100,000$$

- CI_Y represents the cumulative incidence of diagnosed NVAF patients in the year Y
- Y represents the year of interest
- *Count of patients at risk* represents French adult residents from census data in year Y minus count of prevalent diagnosed NVAF patients in year Y

- Overall age-standardized cumulative incidence of diagnosed AF patients in year Y computed as:

$$age - SCI_Y = \frac{\sum_i CI_{i,Y} \times N_{i,Y}}{\sum_i N_{i,Y}} \times 100,000$$

- $age - SCI_Y$ represents the age-standardized cumulative incidence of diagnosed AF patients in year Y
- i represents the age group (<65 years old / 65-74 / 75-79 / \geq 80 years)
- Y represents the year of interest
- $CI_{i,Y}$ represents the crude cumulative incidence of diagnosed AF patients in the age group i in the year Y

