- $N_{i,Y}$ represents the counts of patients at risk (French adult residents from census data in year Y minus count of prevalent diagnosed AF patients in year Y) in the age group i in the year Y

The estimations of the annual standardized incidence and annual prevalence of AF will be also performed according to exposure status (exposed to OAC or unexposed), every year. A patient will be considered exposed to OAC in a given year if the patient presents at least one sequence treatment for an OAC in the corresponding year.

9.7.4.4 Description of the use of oral anticoagulants (OACs) in AF incident patients initiating treatment (AF patients exposed to OAC therapy)

The analysis of the OAC treatment patterns will be descriptive and exploratory in nature.

The date of first reimbursement of any drugs of interest (VKA, apixaban, rivaroxaban, and dabigatran) will be considered as the regimen initiation date and mark the beginning of the identification of the treatment sequence (cf. table VII).

The duration of a prescription will be of 30 days for any drugs of interest. The grace period considered for any drugs of interest considered will be 60 days (30 days and 90 days will be considered for sensitivity analyses).

A treatment sequence will continue until one of the following occurs:

- A regimen switch, defined as the reimbursement of another OAC. The end date of the first treatment sequence is the day before the date of first reimbursement of another OAC.
- Discontinuation of drugs in the treatment sequence: if a period between two consecutive claims is superior to the duration of the treatment of the last claim, plus a permissible gap of at least 60 days (30 and 90 days for sensitivity analyses) then the medication is considered as stopped within the treatment sequence. The date of discontinuation (end date of the treatment sequence) will be fixed at the date of the last claim, plus the treatment duration of this last claim.
- End of follow-up.

The treatment pattern analysis will be providing the following information:

- Number and percentage of patients receiving each of OAC treatment during the follow-up
- Number and percentage of patients who received 1, 2, 3, 4 and 5+ sequence treatment during the follow-up
- Number and percentage of patients who have switched from an OAC to another during the follow-up

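### The SAP's age-standardised AF incidence formula uses each year's own at-risk counts as weights, so it returns the crude incidence, and as written it applies the factor 100,000 twice

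*SAP*

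**What the plan says.** SAP section 9.7.4.3 sets out three quantities for each calendar year Y.

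- **Crude incidence CI_Y:** incident cases divided by the count at risk, times 100,000. The count at risk "represents French adult residents from census data in year Y minus count of prevalent diagnosed NVAF patients in year Y".
- **Standardised incidence age-SCI_Y:** introduced as "Overall age-standardized cumulative incidence of diagnosed AF patients in year Y computed as" Σ(CI_i,Y × N_i,Y) / Σ N_i,Y, times 100,000, over four age groups (<65, 65-74, 75-79, ≥80). Here CI_i,Y "represents the crude cumulative incidence of diagnosed AF patients in the age group i in the year Y".
- **Weight N_i,Y:** it "represents the counts of patients at risk (French adult residents from census data in year Y", minus the prevalent cases of that year, within age group i.

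The same section says results "will be expressed per 100,000 inhabitants".

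Other places describe an external standard. The protocol (Appendix 1, Table A1.5) defines the annual incidence as "standardized on age using the 2019 French population structure and 2020 in sensitivity analyses". SAP Table XXI names INSEE data for the French population as the reference, and footnote 2 of shell Table A12 names the French population. Neither SAP entry gives a year. Table A12 has separate crude and standardised columns for each year.

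**The concern.** Direct standardisation applies each year's age-specific rates to one common age structure, so that differences between years cannot come from a change in that structure. The SAP formula has no common structure. Its weights change every year and are the same counts on which the age-specific rates are based.

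If that removes the standardisation, one deliverable of secondary objective 4 would be mislabelled, and any trend over 2016-2019 (and 2020) would mix change in AF incidence with population ageing. The output would look plausible, so the error could pass unnoticed. The factor 100,000 also seems to enter twice, which would give an impossible value.

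**Working it through.** The documents give a formula and no numerical result, so there is no stated figure to reproduce.

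**1. Algebra.** Let c_i be the incident cases in age group i in year Y and N_i the count at risk. Take CI_i = c_i / N_i as a proportion. Then

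Σ(CI_i × N_i) / Σ N_i = Σ(c_i / N_i × N_i) / Σ N_i = Σ c_i / Σ N_i.

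The right-hand side is the crude incidence before scaling. It holds for any data. A check in exact arithmetic on 10,000 random four-group data sets found equality in every one. It also holds for the exposed and unexposed rows of Table A12 if they use the same at-risk denominator.

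**2. The factor 100,000.** The SAP's only formula for crude cumulative incidence includes × 100,000, and CI_i,Y is described in words as that same quantity within an age group. On that reading the standardised formula gives Σ c_i / Σ N_i × 100,000 × 100,000. For scale, a rate of 410 per 100,000 (the figure cited in the background sections) would print as 410 × 100,000 = 41,000,000 per 100,000. If CI_i,Y is a proportion, the final factor is correct.

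**3. Worked example.** All inputs are assumptions for illustration. None comes from the documents. Age-specific rates are the same in both years.

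| Age group | Rate per 1,000 | At risk 2016 (millions) | Cases 2016 | At risk 2019 (millions) | Cases 2019 |
|---|---|---|---|---|---|
| <65 | 0.8 | 39.5 | 31,600 | 39.3 | 31,440 |
| 65-74 | 7 | 6.3 | 44,100 | 7.0 | 49,000 |
| 75-79 | 14 | 1.95 | 27,300 | 2.0 | 28,000 |
| ≥80 | 25 | 3.5 | 87,500 | 3.7 | 92,500 |
| Total | | 51.25 | 190,500 | 52.0 | 200,940 |

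- Crude: 190,500 / 51.25 million = 371.7 per 100,000 in 2016; 200,940 / 52.0 million = 386.4 in 2019.
- SAP formula, factor applied once: 371.7 and 386.4, identical to crude.
- SAP formula, factor applied twice: 37,170,732 for 2016.
- Fixed weights, with the 2019 at-risk counts standing in for the 2019 structure: 200,940 / 52.0 million = 386.4 in both years.

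The fixed-weight result is flat, as it should be when no age-specific rate has changed. The SAP formula shows a rise of 386.4 − 371.7 = 14.7 per 100,000 that is due to ageing alone.

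**The case against.** Four points can be made for the plan.

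- **The intent is clear elsewhere.** The protocol names the 2019 structure, and SAP Table XXI and the Table A12 footnote name the French population, so a programmer might use the right standard anyway. This shows a conflict between formula and text, but it does not cure it. The SAP gives no reference year, and a reader could take N_i,Y to be the French population that the footnote means.
- **The doubled factor is partly notation.** CI_i,Y is defined in words without a scale. Read as a proportion, the last factor is right and only a clarification is needed. Read literally, the result exceeds 100,000 per 100,000 and would be noticed. This stands: the factor is the lesser of the two errors.
- **The scope is narrow.** Only the standardised columns of Table A12 are affected, in a descriptive secondary analysis. Crude incidence, prevalence (Table A13), the event rates of the primary objective (standardised to the exposed group) and the Cox models do not use this formula. This also stands.
- **Comparison with the cited 410 per 100,000 is not a strong argument.** The documents do not give that rate's standard population, and it covers newly treated patients only. The finding does not depend on it.

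None of these touches the identity itself.

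**Conclusion.** The formula is wrong as written and must be corrected. That it returns the crude incidence is an exact identity from the SAP's own definitions and needs no assumed data. It contradicts the fixed standard in the protocol. The doubled factor follows from the SAP's only definition of crude cumulative incidence, and falls away only if CI_i,Y is declared a proportion.

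The consequence is certain for Table A12: each standardised column would equal its crude column (factor applied once), with ageing left in the trend. How much ageing would distort the real trend cannot be derived from the documents. The 14.7 per 100,000 above depends on the assumed counts and rates.

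**What to change.** In SAP section 9.7.4.3:

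1. Replace the weights N_i,Y by fixed standard counts W_i: age-SCI_Y = Σ(CI_i,Y × W_i) / Σ W_i, with W_i the 2019 French population by age group. State that the adult population is used, since the protocol does not say so and the study includes adults only.
2. For the 2020 sensitivity analysis, use the 2020 structure as the protocol states, and apply it to every year shown in that analysis so that no table mixes two standards. Note that the 2016-2019 values will then differ from the main analysis for that reason alone.
3. Apply the factor once: either keep CI_i,Y per 100,000 and delete the final factor, or define CI_i,Y as a proportion and keep it.
4. Compute the confidence interval from the same weights, for example with variance Σ (W_i / Σ W_i)² × c_i / N_i,Y² on the proportion scale, treating the case counts as Poisson.
5. Put the reference year in Table XXI and in footnote 2 of Table A12.

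The cost is one formula, its interval and two labels. The INSEE data are already planned, and no other analysis changes.

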9.2.1.2 Index Date

Depending on the date of first evidence of AF over the study period, AF patients will be included at the following dates:

- On 1st January 2016 for **prevalent AF patients** (i.e., patients diagnosed AF during the historical period);
- On the first date of evidence of AF (first date of diagnosis of AF identified either by a LTD or the start date of a hospitalization, or the first date of OAC dispensation) for **incident AF patients**.

A patient will be considered exposed to OAC at the time of his/her inclusion if at least one dispensation of OAC is issued within 30 days after inclusion (including date of inclusion). In such a case, the index date will be the date of the first dispensation of OAC (cf. Appendix 1).

Otherwise, if no dispensation of OAC will be identified within 30 days from inclusion, the index date will be the date of inclusion.

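### AF incidence by OAC status (SAP 9.7.4.3, Table A12) classifies exposure by calendar year, so the time allowed to become exposed depends on the month of diagnosis; the resulting bias cannot be signed

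*SAP*

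**What the plan says.** Objective 4 is the annual incidence and prevalence of non-valvular AF in patients exposed and unexposed to OAC. SAP 9.7.4.3 applies one exposure rule to both measures: "The estimations of the annual standardized incidence and annual prevalence of AF will be also performed according to exposure status", every year. The rule is: "A patient will be considered exposed to OAC in a given year if the patient presents at least one sequence treatment for an OAC" in that same year. Footnote 3 of Table A12 (incidence) and the matching footnote of Table A13 (prevalence) repeat it. A treatment sequence starts at the first delivery (Table VII), so a January dispensing creates no sequence in the previous year. The incidence numerator is the "count of incident diagnosed NVAF patients in year Y".

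SAP 9.2.1.2 has a different rule for exposure at inclusion. A patient is exposed "if at least one dispensation of OAC is issued within 30 days after inclusion", with no calendar limit. "In such a case, the index date will be the date of the first dispensation of OAC". Inclusion is the first evidence of AF: "first date of diagnosis of AF identified either by a LTD or the start date of a hospitalization", or otherwise the first OAC dispensing. Table XI and the characteristics tables (A4-A9) use exposure at the index date.

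**The concern.** A calendar-year rule suits prevalence, where the question is whether a patient was treated during the year. For incidence, patients enter on different days and all are judged on 31 December. Patients in the same row of Table A12 are therefore classified on windows of very different length.

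Two misclassifications follow, measured against a fixed window from diagnosis:

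- A patient diagnosed in late December and dispensed promptly in January is counted as unexposed incident AF.
- A patient diagnosed in January and first treated many months later is counted as exposed.

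The study's stated rationale is the lack of French data on AF without OAC, so the unexposed row of Table A12 will be read closely. As planned, it describes neither AF untreated at diagnosis nor AF untreated over a fixed follow-up. SAP 9.2.3.3.2 draws objective 4 and the cross-sectional part of objective 2 from the same incident patients. The report would then show two different exposed/unexposed splits of those patients under the same labels (Table A12 against A4-A6). No sensitivity analysis in 9.7.6 or under Table A12 addresses this; changing the grace period does not move a first delivery across a year-end.

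**Working it through.** The documents state no figure on this point, so there is none to reproduce.

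**Step 1. The two rules applied to dated cases** (year set by diagnosis date)

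| Diagnosis | First OAC | 30-day rule (9.2.1.2) | Calendar-year rule (9.7.4.3) |
|---|---|---|---|
| 20 Dec 2017 | 10 Jan 2018 (day 21) | exposed | unexposed, 2017 |
| Jan 2017 | Jun 2017 | unexposed | exposed, 2017 |

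The 30-day window crosses the year-end for diagnoses from 2 to 31 December: 30/365 = 8.2% of days.

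**Step 2. Year-end error alone.** Let m be the mean delay in days from inclusion to first dispensing among patients exposed within 30 days, and p their share of incident AF. With diagnoses spread evenly over the year, m/365 of these patients cross 31 December. The relative increase in the unexposed count is (m/365) × p/(1−p). Neither m nor p is in the documents. m must average over all exposed patients, including those identified by OAC initiation, whose delay is zero.

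- m = 3, p = 0.60: (3/365) × 1.50 = 1.2%
- m = 7, p = 0.70: (7/365) × 2.33 = 4.5%
- m = 10, p = 0.70: (10/365) × 2.33 = 6.4%
- m = 10, p = 0.80: (10/365) × 4.00 = 11.0%

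On wider assumptions (p = 0.50-0.85, m = 3-15) the range is 0.8% to 23%.

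**Step 3. Late starters, the opposite error.** Let q be the share of all incident patients who first receive an OAC on days 31-365 (also not given). If those starts are uniform, the chance that one falls in the diagnosis year is the mean of (365−k)/365 over k = 31 to 365, which is 167/365 = 0.458. The net relative change in the unexposed count is (p·m/365 − 0.458q)/(1−p). At p = 0.70 and m = 7:

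- q = 0: +4.5%
- q = 5%: (0.0134 − 0.0229)/0.30 = −3.2%
- q = 10%: (0.0134 − 0.0458)/0.30 = −10.8%

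The errors cancel when q = (p·m/365)/0.458. That is 1.1% at p = 0.60, m = 3; 2.9% at p = 0.70, m = 7; and 4.8% at p = 0.80, m = 10. A small share of late starters is therefore enough to reverse the sign. With q = 5-10% on the wider grid, the net change runs from about −26% to +8%.

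**Step 4. If the year followed the index date instead.** The December case would move to 2018 as exposed and the year-end error would vanish. The late-starter error would remain.

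**The case against.** **No rule is broken.** A reader might infer that 9.7.4.3 violates the SAP's own 30-day rule. The text does not support that. Section 9.2.1.2 defines exposure at the time of inclusion and refers to Appendix 1, whose title covers objectives 1, 2, 3 and 7, not 4. Objective 4 has its own explicit rule, disclosed in the table footnotes. This stands: there are two definitions that the SAP does not reconcile.

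**Not all other tables use the 30-day split.** A reader might also infer a mismatch with the primary-objective tables. Tables A2-A3 divide person-time into exposed and unexposed periods, so the mismatch is with A4-A9 only.

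**The 30-day cut-off is itself a choice.** Protocol 3.5.2 sets no window: exposure is an initiation, and unexposed means a first diagnosis without OAC. Calling a January diagnosis treated in November exposed fits that wording. This stands as an argument about where to put the cut-off. It does not justify a cut-off that varies with the month of diagnosis.

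**The year is not pinned down.** Diagnosis date is the plainer reading of the numerator, but Tables A4-A6 are reported per year at index date. This uncertainty is itself a reason to state which date applies.

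**Limited reach.** Objective 4 is secondary and descriptive. The overall incidence row, the primary event rates and the Cox models do not use this rule. With stable prescribing delays the year-end effect recurs each year, so trends would be little affected. That is fair, although the study also sets out to describe changes in management after the 2018 recommendations, so stable delays cannot be taken for granted.

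**Conclusion.** The point holds for the exposed and unexposed incidence rows of Table A12, provided the year is set by diagnosis date. The window for becoming exposed then varies from about 12 months to a day or so, and patients are misclassified in both directions.

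It is tempting to conclude that unexposed AF incidence is overstated by 1-11%. The documents do not support that. The figure covers the year-end error only, under an assumed 3-10 day mean delay over all exposed patients and 60-80% exposed. Late starters push the other way and may dominate, so the net bias cannot be signed. Only cases found by LTD or hospital stay are affected, because OAC-identified cases are included on the dispensing date.

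The change should be made: it removes an avoidable misclassification from a result the study is meant to supply, using a variable the SAP already defines.

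**What to change.** 1. In 9.7.4.3 and Table A12, assign each incident patient to the year of the inclusion date and take exposure from the 30-day rule in 9.2.1.2. Keep the calendar-year rule for prevalence only (Table A13).
2. State that January 2020 dispensings, which lie within the extraction, are used solely to classify December 2019 inclusions. This needs an explicit exception, because protocol 3.1.2 excludes 2020 data from the main analyses and SAP 9.2.1.4 ends main follow-up on 31 December 2019.
3. In the 2020 sensitivity analysis, note that the 30-day window is truncated for December 2020 inclusions, since the extraction ends on 31 December 2020.
4. Label the Table A12 rows as exposed or unexposed within 30 days of inclusion.

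The cost is a short text change, a footnote and the stated exception; no new variable is needed. The downside is that patients starting an OAC after day 30 count as unexposed at diagnosis, which the row label should make plain.
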